1 PROTOCOL SYNOPSIS**TITLE:**

Premaxillary injection for perioral rejuvenation and upper lip enhancement

INDICATION:

Premaxillary injection performed via cannula technique for perioral rejuvenation

SAMPLE SIZE:

20

NUMBER OF CENTERS:

One

PURPOSE:

To determine if subjects who receive premaxillary injection demonstrate an increase in nasal tip projection and an associated increase in upper lip projection, and vermillion height.

SUBJECTION SELECTION:

A total of 20 subjects who display signs of perioral aging or poor upper lip projection

PROCEDURE:

This is an open-label, prospective, post market study to assess the effect of premaxillary hyaluronic acid filler injection on nasal tip projection and upper lip position.

The study will enroll and treat a total of 20 subjects who are filler naïve and do not have any history of rhinoplasty, recent upper lip augmentation <12 months, lip lift or other surgical procedures involving the upper lip, chin augmentation and orthognathic surgery. Patients in study are restricted from perioral neurotoxin, peri oral ablative resurfacing, facial cosmetic surgery, all subdermal directed aesthetic treatments or filler treatment other that which is dictated in the protocol during the course of the study.

Subjects, who fulfill all eligibility criteria, will undergo pre-treatment standardized 2D portrait photography. From the profile image, baseline nasal projection measurements will be documented according to Goode's ratio. Additionally, baseline upper lip position will recorded by measuring the Z-angle, which is the intersection of the Frankfort horizontal line and the profile line as described by Merrifield. From the straight portrait image, the ratio of the upper lip vermillion height to the lower lip vermillion height will be documented. Subjects will then be injected with a maximum of 4 syringes of Restylane® Defyne to treat their premaxillary space per the discretion of the Principal Investigator (PI). If optimal correction result (OCR) has not been achieved additional touch-up injections of Restylane® Defyne may be injected 2 weeks post treatment visit to achieve OCR as per PI discretion.

Post OCR visits will be performed at 4 weeks following premaxillary injections. Subjects will be followed to assess any treatment-related adverse events (such as pain, nodules, swelling, redness, bruising, tenderness, itching, and headache) as well as pigmentation changes and/or keloid formation. Each subject will then be photographed with standardized photographs in a similar fashion as pre-treatment and the same measurements will be recorded.

Upon study culmination, pre-treatment and 1-month post OCR photographs will be assessed. Each patient will be evaluated to determine if nasal tip projection was increased causing an increase in upper lip projection. Additionally, the vermilion ratios will be compared to evaluate for change in upper lip vermilion height.

STUDY DURATION:

Each subject will undergo screening assessment of eligibility criteria, pre-treatment photography, and if eligible for treatment, injections of the premaxillary area. All enrolled subjects will be followed up to 1-month post OCR visit to evaluate the injections effect on nasal tip projection and upper lip projection.

OBJECTIVES:

The Primary Objective of this study is to determine the increase in nasal tip projection (measured by Goode's ratio) and the increase in upper lip projection (measured by the Z-angle) following perioral rejuvenation with premaxillary hyaluronic acid filler injections.

The Secondary Objective of this study is to assess the change in upper lip height by comparing the pre and post-treatment injection ratio of upper lip vermilion height to lower lip vermilion height.

CLINICAL HYPOTHESES:

Subjects who are treated with premaxillary injection will demonstrate an increase in nasal tip projection and have an associated increase in upper lip projection. Additionally, the upper lip will demonstrate an increase in upper lip vermilion height. As a result, the single injection site will address multiple factors that contribute to perioral aging.

2 BACKGROUND

Earlier this year, Cerrati and [name] demonstrated the causal relationship between nasal tip projection and upper lip projection. This new correlation, which was discovered in examining post-surgical rhinoplasty patients, was published last month in *JAMA Facial Plastic Surgery*. As the nasal tip was projected, a statistically significant increase in the upper lip projection was

measured. For tip projection, Goode's ratio was used. This value is defined as the nasal height over the nasal length. Upper lip projection was measured by the Z-angle, which is created by the Frankfort horizontal plane and the profile line. A change in the angle to a more acute value on postoperative photographs would indicate an increase in upper lip projection. Additionally, the study demonstrated a trend toward an increase in upper lip vermilion height. By applying this new correlation, [name] was able to recreate the findings in a small subset of aging patients using hyaluronic acid filler.

While the perioral aging process has been well described in the literature, the treatment options have remained limited. The most common attempt at rejuvenation is injection of hyaluronic acid filler into the lips and philtral columns. However, studies have shown that changes occur at deeper levels. Within the orbicularis oris muscle, the curvature relaxes resulting in an overall increase in lip length. More importantly, selective bony resorption occurs in specific areas of the facial skeleton including the maxilla. The retrusion of the maxilla along with widening of the piriform aperture contribute to the overlying soft tissue changes in the nose.

The premaxillary injection adds a new tactic for addressing perioral aging. The single injection will allow treatment of the fundamental cause of aging by re-building the foundation of the face. Treatment will provide patients with nature appearing facial rejuvenation. Since the aging process affects both the nose and the upper lip, these patients receive a significant benefit, both aesthetically and cost-effectively.

3 STUDY OBJECTIVES

The Primary Objective of this study is to determine the increase in nasal tip projection (measured by Goode's ratio) and the increase in upper lip projection (measured by the Z-angle) following perioral rejuvenation with premaxillary hyaluronic acid filler injections.

The Secondary Objective of this study is to assess the change in upper lip height by comparing the pre and post-treatment injection ratio of upper lip vermilion height to lower lip vermilion height.

5 STUDY DESIGN

This is an open-label, prospective, postmarket study to assess the effect of premaxillary hyaluronic acid filler injection on nasal tip projection and upper lip position.

The study will enroll and treat a total of 20 subjects who are filler naïve and do not have any history of rhinoplasty, recent, 6 months upper lip augmentation, lip lift or other surgical procedures involving the upper lip, chin augmentation and orthognathic surgery. Patients in study are restricted from perioral neurotoxin or ablative resurfacing, facial cosmetic surgery, all subdermal directed aesthetic treatments or filler treatment other than which is dictated in the protocol during the course of the study.

Subjects, who fulfill all eligibility criteria, will undergo pre-treatment standardized 2D portrait photography. From the profile image, baseline nasal projection measurements will be documented according to Goode's ratio. Additionally, baseline upper lip position will be recorded by measuring the Z-angle, which is the intersection of the Frankfort horizontal line and the profile line as described by Merrifield. From the straight portrait image, the ratio of the upper lip vermilion height to the lower lip vermilion height will be documented. Subjects will then be injected with a maximum of 4 syringes of Restylane® Defyne to treat their premaxillary space per the discretion of the Principal Investigator (PI). If optimal correction result (OCR) has not been achieved additional touch-up injections of Restylane® Defyne may be injected 2 weeks post treatment visit to achieve OCR as per PI discretion.

Post OCR visits will be performed at 4 weeks following premaxillary injections. Subjects will be followed to assess any treatment-related adverse events (such as pain, nodules, swelling, redness, bruising, tenderness, itching, and headache) as well as pigmentation changes and/or keloid formation. Each subject will then be photographed with standardized photographs in a similar fashion as pre-treatment and the same measurements will be recorded.

Upon study culmination, pre-treatment and 1-month post OCR photographs will be assessed. Each patient will be evaluated to determine if nasal tip projection was increased causing an increase in upper lip projection. Additionally, the vermilion ratios will be compared to evaluate for change in upper lip vermilion height.

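### The Synopsis and Section 5 promise a per-patient finding that tip increase caused lip increase, which this uncontrolled design cannot supply

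*Combined protocol and SAP*

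**What the plan says.** Section 5 states: "Each patient will be evaluated to determine if nasal tip projection was increased causing an increase in upper lip projection". The Synopsis carries the same sentence, including the words "nasal tip projection was increased causing an increase in upper lip projection". In both places it describes a planned evaluation of the photographs once the study is complete.

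The other statements of aim are not causal between nose and lip:

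- Section 3 makes the primary objective the increase in tip projection by Goode's ratio "and the increase in upper lip projection (measured by the Z-angle) following perioral rejuvenation".
- Section 5 opens by saying that the study is "to assess the effect of premaxillary hyaluronic acid filler injection on nasal tip projection and upper lip position".
- The Study Duration part of the Synopsis says that follow-up is "to evaluate the injections effect on nasal tip projection and upper lip projection".
- The Purpose is to see whether subjects "demonstrate an increase in nasal tip projection and an associated increase in upper lip projection". The Clinical Hypotheses also use *associated*, and end by saying that "the single injection site will address multiple factors that contribute to perioral aging".

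Section 2 (Background) describes the tip-to-lip relationship in a prior rhinoplasty study as causal, and also as a correlation: "This new correlation, which was discovered in examining post-surgical rhinoplasty patients".

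On analysis, Section 11.2 names a comparison of photographs before and after treatment, and Section 11.3 names a paired *t* test and nothing else. Section 9.1 defines both measures and says that a more acute Z-angle means more lip projection. The Injection Techniques text in Section 7 places the filler between the maxilla and the lip muscle, across the span of the alar bases.

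**The concern.** The sentence commits the study to deciding, patient by patient, that a change in the nose produced a change in the lip. Two things are missing. The plan does not say how the decision is to be made, and the design has no feature that could separate that pathway from the filler acting on each structure directly.

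What is at stake is the wording of the result. Someone following the sentence would have two measured changes per patient and no criterion. One plausible course is to call a patient positive when both measures rise and to present the count as support for causation. That rule is my assumption; the documents do not state it. It is used below only to show how little such a count would mean.

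**Working it through.** **Inputs.** From the documents: n = 20, all treated (Synopsis, Section 5). They give no effect size, SD, correlation or threshold for an increase, and no derivation of the 20, so there is no figure of the plan's own to reproduce. Assumed: normal within-patient changes in SD units, the same standardised mean change d for tip and lip, and any change in the favourable direction counted as an increase.

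**Step 1: what the paired *t* test uses.** Applied to each measure, it depends only on the mean and SD of that measure's 20 changes. Re-pairing one patient's tip change with another patient's lip change leaves both results the same. The test therefore carries no information on whether the two changes are linked.

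**Step 2: patients with both increases when there is no link.** Under independence, P(both) = Φ(d) × Φ(d), and the expected count is 20 × Φ(d)².

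| d (SD) | Φ(d) | Φ(d)² | Expected of 20 |
|---|---|---|---|
| 0 | 0.500 | 0.250 | 5.0 |
| 0.5 | 0.691 | 0.478 | 9.6 |
| 0.66 | 0.745 | 0.556 | 11.1 |
| 1.0 | 0.841 | 0.708 | 14.2 |

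The value 0.66 is the effect that a two-sided 5% paired *t* test detects with 80% power at n = 20. With no mean effect at all, the chance that at least one patient shows both increases is 1 − 0.75^20 = 0.997. With a true correlation of 0.5 at d = 0.66, P(both) is 0.614, or 20 × 0.614 = 12.3 patients. That is about one more than under independence.

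**Step 3: could a better rule separate the explanations?** Take two models with unit SDs.

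- Model A, no nose-to-lip path: tip and lip changes each have mean d and share a common factor that explains half the variance of each. Their correlation is 0.5.
- Model B, tip drives lip: tip change has mean d, and lip change = 0.5d + 0.5 × tip change + error with variance 0.75. The lip mean is 0.5d + 0.5d = d, its variance is 0.25 + 0.75 = 1, and the correlation is 0.5.

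The joint distribution is the same in both. Simulation at d = 0.8 agrees (20,000 trials of 20): both tests significant in 86.8% (A) and 87.2% (B), patients with both up 67.0% and 67.3%, mean correlation 0.49 in each. No analysis of these two changes alone can tell A from B.

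**Step 4: what a correlation could show.** By Fisher's z, an observed r of 0.5 gives atanh(0.5) = 0.549, with half-width 1.96/√17 = 0.475. The 95% CI is tanh(0.074) to tanh(1.025), that is 0.07 to 0.77. For 80% power the true r must be about tanh(2.80/√17) = 0.59.

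**Step 5: would adjusting for injected volume settle it?** Suppose volume explains 25% of the variance of each change, a second shared factor explains another 25%, and there is no nose-to-lip path. The partial correlation given volume is 0.25/0.75 = 0.33. Simulation puts the chance of a significant adjusted result at about 29%. The Fisher approximation is close: atanh(0.33) × √16 = 1.39, and P(Z > 1.96 − 1.39) = 0.28. With a second factor of 15%, the chance is about 13%. Adjustment gives about 5% only if volume is the sole shared cause, acts linearly and is measured without error.

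**The case against.** The strongest reply is that this is one loosely worded narrative sentence. Sections 3, 9.1 and 11.2 and the opening of Section 5, which fix what is measured and compared, ask about the injection's effect on each measure or about change in the photographs. None asks whether one change drives the other. Because Section 2 treats the tip-to-lip link as already shown, *causing* may only repeat an assumed mechanism. This stands as a limit on the weight of the point. It does not remove it, because the sentence is phrased as something the study will determine in each patient.

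Second, Section 9.1 does supply part of a rule. It gives the direction of a lip increase, and it chose the Z-angle because nasal changes do not enter its calculation. That is correct, and it avoids arithmetic coupling with Goode's ratio. It does not exclude a common cause, and it sets no threshold and no joint criterion.

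Third, treatment is not literally one deposit: access is bilateral, the material is fanned, and a touch-up is allowed. The argument needs only that the filler goes to the same space, which the Injection Techniques text says.

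Fourth, no section mentions counting patients with both increases. That is also true, and the counts above are illustrations.

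A reader might infer that the plan is deficient for lacking a correlation analysis. The documents do not support that. *Associated* in the Purpose and Clinical Hypotheses can mean accompanying as easily as linked, and the primary objective needs no correlation.

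**Conclusion.** The point holds as a minor one about interpretation. As written, the sentence in the Synopsis and Section 5 leads to a causal conclusion that the design cannot support, whatever rule is used. The qualitative part rests only on the documents: no control, every subject treated, one filler space, a paired *t* test. The counts rest on independence, normality, equal standardised effects and a zero threshold, all assumed.

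Two stronger readings should be resisted. A reader might infer that the primary analysis is undermined. It is not, on this ground: Section 3 asks for two increases, and a paired test on each addresses that. A reader might also infer that a volume-adjusted correlation would rescue the causal claim. It would not. Filler placement and head position in the photographs are other possible shared causes, and no claim that adjustment restores a 5% error rate should be made.

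**What to change.** In the Synopsis and in Section 5, replace the sentence with wording such as: *Each patient will be assessed for a rise in nasal tip projection and, separately, for a rise in upper lip projection, between pre-treatment and 1 month post OCR. The study draws no conclusion that change at the tip caused change at the lip.* This keeps the per-patient description and drops only the causal step. It changes one sentence in two places and leaves visits, measurements, sample size and the primary test alone. The price is a weaker claim than *causing*.

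Optionally, if the sponsor means *associated* as a link, add to Section 11.3 the correlation of change in Goode's ratio with sign-reversed change in Z-angle (a smaller angle means more projection), with a 95% CI. Label it exploratory and descriptive, and state that it may reflect any shared cause, including injected volume, filler placement and head position in the photographs. It costs one statistic, and the interval will be wide at n = 20. The correction does not depend on it.

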6 SUBJECT SELECTION

A total of 20 subjects.

All Subjects must comply with the following inclusion and exclusion criteria:

6.1 Inclusion Criteria

1. Subjects Age 21 to 70.
2. Subjects who demonstrate signs of perioral aging or poor upper lip projection.

6.2 Exclusionary Criteria

1. Subjects who plan to undergo peri oral neurotoxin treatments or ablative skin treatments, or have had either of these treatments in the previous 6 months, other injectable filler treatments during the course of the study.
2. Subjects who are pregnant or nursing.
3. Subjects with a known allergy or sensitivity to any component of the study ingredients.
4. Any history of nasal filler injections.
5. Recent history of upper lip augmentation (surgical and non-surgical) within the last 12 months.
6. Any history of lip lift or other surgical procedures involving the upper lip.
7. Any history of chin augmentation (surgical and non-surgical).
8. Any history of orthognathic surgery.
9. Any history of bleeding disorders (iatrogenic or otherwise).
10. Current history of chronic drug or alcohol abuse.
11. Concurrent therapy that, in the investigator's opinion, would interfere with the evaluation of the safety or efficacy of the study product (i.e. immunosuppressive therapy).
12. Subjects who, in the Investigator's opinion, have a history of poor cooperation, noncompliance with medical treatment or unreliability.

7 TREATMENT AND STUDY MATERIAL SUPPLIES

7.1 Description of Study Supplies and Handling

7.1.1 Packaging and Labeling

7.1.1.1 Restylane® Defyne

Injectable Gel with 0.3% Lidocaine

2.1.2 Method of Application

Pre-treatment Guidelines

Prior to treatment, the patient should avoid taking aspirin, nonsteroidal anti-inflammatory medications, St. John's Wort, or high doses of Vitamin E supplements. These agents may increase bruising and bleeding at the injection site.

Treatment Procedure

1. It is necessary to counsel the patient and discuss the appropriate indication, risks, benefits and expected responses to the *Restylane® Defyne* treatment. Advise the patient of the necessary precautions before commencing the procedure.
2. Assess the patient's need for appropriate anesthetic treatment for managing comfort, i.e., topical anesthetic, local or nerve block.
3. The patient's face should be washed with soap and water and dried with a clean towel. Cleanse the area to be treated with alcohol or another suitable antiseptic solution.
4. Sterile gloves are recommended while injecting *Restylane® Defyne*.
5. Attach the syringe to a 22-gauge cannula, which provides additional safety when injecting in this area. Before injecting, press rod carefully until a small droplet is visible at the tip of the cannula.
6. Using a 20-gauge needle, a small access point is created for the cannula. The access points are located within the superior portion of the nasolabial folds bilaterally
7. Inject *Restylane® Defyne* applying even pressure on the plunger rod. It is important that the injection is stopped just before the cannula is pulled out of the skin to prevent material from leaking out or ending up too superficially in the skin.
8. Only correct to 100% of the desired volume effect. Do not overcorrect. The degree and duration of the correction depend on the character of the defect treated, the tissue stress at the implant site, the depth of the implant in the tissue and the injection technique.

9. Typical usage for each treatment session is specific to the amount of correction desired.

Injection Techniques

1. *Restylane® Defyne* can be injected by a number of different techniques that depend on the treating physician's experience and preference, and patient characteristics.

2. Given the close proximity to large vessels within the premaxillary space, the cannula technique is advocated. The use of large cannulas (22-gauge) helps minimize the risk of vascular injury. The cannulas are introduced through the skin by a small puncture site created by a slightly larger hypodermic needle.

3. Once the cannula is inserted, linear threading (includes retrograde and antegrade) is accomplished along with fanning to produce an even layer of material. The material should be deposited in the premaxillary space, which is located between the maxilla and the orbicularis oris muscle spanning between the alar bases.

8 STUDY PROCEDURES

8.1 Screening Visit

The PI and/or designee is responsible for keeping a record of all subjects screened for entry into the study and those subjects that were excluded, including exclusionary reason.

The following procedures will be performed:

1. The PI and/or designee is responsible to evaluate and confirm that a subject meets inclusionary/exclusionary criteria.
2. Subjects must provide signed informed consent with confirming signature from investigator/site designee.
3. Subject undergo standard 2D digital portrait photography.

8.2. Visit 1: Baseline/Treatment Procedures

The following procedures will be performed:

1. The injection area will be wiped with a Benzalkonium Chloride towlette.
2. A topical anesthetic containing lidocaine (30%) will be applied to anesthetize injection areas Or subject may choose to receive a nerve block to numb the treatment area.

3. The subject will be injected with *Restylane® Defyne* in a volume sufficient to deliver satisfactory cosmetic results (not to exceed 4mL/4syringes total).
4. The volume injected into each area will be recorded.

